### **3.3 Exclusion Criteria**

- 3.3.1 Thrombolysis within 6 weeks prior to enrollment
- 3.3.2 Patients with statin use within 6 weeks of enrollment
- 3.3.3 Patients with known allergy or intolerance to statins or statins are contraindicated for any other reasons
- 3.3.4 Patients with baseline aspartate aminotransferase (AST), alanine aminotransferase (ALT), or total bilirubin  $\geq 2.0 \times$  ULN (upper limit of normal)
- 3.3.5 Pregnant or breastfeeding females are excluded
- 3.3.6 Any malignancy diagnosed within the preceding 2 years, except for squamous cell carcinoma or basal cell carcinoma of skin treated with local resection only, or carcinoma *in situ* of the cervix
- 3.3.7 Incarcerated patients are excluded from the study due to the inherent difficulties in maintaining close follow-up for study purposes in patients who are incarcerated.

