## 5.0 Treatment plan: atorvastatin vs placebo

After randomization, patients on the statin arm will start the assigned study drug (atorvastatin) for a total of 9 months, in addition to the standard of care (anticoagulation). Atorvastatin will be prescribed through patients' pharmacy of choice. It will be taken once a day in a tablet form. Pill count and patient self-report compliance diary will be reviewed at each visit. All the attempts will be made to continue atorvastatin for entire 9 months, however, if a patient needs to stop atorvastatin prior to the intended period for any reasons (for example, side effects), it will be documented, but they are allowed to remain in the study for blood tests and clinical follow up. At the end of the study, the decision of whether patients should remain on atorvastatin or not will be left to the treating physicians.

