## 6.0 Study calendar

	Initial visit	3 month 	9 month 
Singed informed consent	x		
Medical/treatment history	x	x	x
Physical examination	x	x	x
Vital signs	x	x	x
CBC with diff	x	x	x
Chemistry, including liver function tests	x	x	x
Fasting lipid profiles	x	x	x
hs-CRP	x	x	x
D-dimer	x	x	x
Urine <math>\beta</math>-hCG	x		
Thrombin generation assay	x	x	x
IL-6, IL-8, TNF-<math>\alpha</math>	x	x	x
Lipidomic profiles	x	x	x
Doppler ultrasound of bilateral lower extremities		x	
Prescription of statins	x	x	

All scheduled visits are allowed a window of +/- 21 days

CBC includes: white blood cells with differential, hemoglobin, red blood cells, and platelets

Chemistry and liver function tests include: sodium, potassium, carbon dioxide, glucose, BUN, creatinine, calcium, total protein, albumin, bilirubin, alkaline phosphatase, AST and ALT

Required only in women of child-bearing potential

Lipidomic profiles includes free fatty acids, lipoprotein-associated phospholipase A2, pro-inflammatory eicosanoids

Prescription of statins only in the statin arm

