### **9.2 Subsequent Follow-up and Correlative Laboratory Studies**

9.2.1 All enrolled patients will be seen on enrollment and at month 3 and 9.

9.2.2 The following laboratory studies will be obtained at each follow-up visit:

- CBC (complete blood count), platelet count
- chemistry panel (Na, K, Cl, CO2, Cr, BUN, Ca, and glucose),
- liver function tests (AST, ALT, ALP, total and direct bilirubin)
- d-dimer
- high-sensitivity C-reactive protein (hs-CRP)
- fasting lipid profiles (LDL, HLD, TG, total cholesterol)

*Research labs:*

- thrombin generation assay
- IL-6, IL-8, tumor necrosis factor (TNF)- $\alpha$
- lipidomic profiles including free fatty acids, lipoprotein-associated phospholipase A2, pro-inflammatory eicosanoids
- plasma levels and RNA expression of tissue factor (TF), tissue factor pathway inhibitor (TFPI), and other clotting factors

9.2.3 A follow up Doppler ultrasound will be obtained at month 3 as standard of care in all patients to evaluate residual vein thrombosis.

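### Atorvastatin is prescribed again at month 3 without a repeat pregnancy test, and the stop rule in 11.2 does not name pregnancy: a minor, low-cost safety gap

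*Combined protocol and SAP*

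**What the plan says.** The main text is the study calendar in Section 6. Its urine beta-hCG row is marked under the initial visit and left empty at months 3 and 9; the footnote reads "Required only in women of child-bearing potential". Its statin row is marked at the initial visit and again at month 3, with the footnote "Prescription of statins only in the statin arm". Visit timing is loose: "All scheduled visits are allowed a window of +/- 21 days".

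The laboratory lists agree with the calendar. Section 9.1.1 (enrollment) includes beta-hCG. Section 9.2.2, introduced by "The following laboratory studies will be obtained at each follow-up visit", does not.

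The surrounding text is as follows.

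- **3.3.5:** "Pregnant or breastfeeding females are excluded". No reason is given, and the criterion applies to both arms.
- **3.3.3**, the criterion specific to statins: "Patients with known allergy or intolerance to statins or statins are contraindicated for any other reasons". It also operates at entry.
- **5.0:** "patients on the statin arm will start the assigned study drug (atorvastatin) for a total of 9 months". The same section provides for early stopping, "if a patient needs to stop atorvastatin prior to the intended period for any reasons", with documentation and continued follow-up.
- **11.2:** physicians evaluate patients for side effects at every visit. Atorvastatin is withdrawn for new transaminitis, CK above three times the upper limit of normal, or significant symptoms. Pregnancy is not named.
- **12.2:** a birth defect counts as a serious adverse event, and there is a general category for other significant hazards.

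**The concern.** The trial checks for pregnancy before it writes the first atorvastatin prescription but not before it writes the second, which covers most of the course. If the schedule is followed exactly, a woman who has conceived since enrollment and does not know it can be given the second prescription.

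The protocol treats its other laboratory-checked exclusion differently. Liver function is an entry criterion (3.3.4), is measured again at months 3 and 9, and has a named stop rule in 11.2. Pregnancy has neither a repeat check nor a named rule, and the visible text contains no contraception requirement.

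Only participant safety is at stake. The primary comparison of thrombin peak and endogenous thrombin potential is untouched.

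**Working it through.** **1. Is the single test a table-reading artefact?** No. Three places can be set side by side:

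| Place | Beta-hCG at entry | Beta-hCG at month 3 | Statin prescription at month 3 |
|---|---|---|---|
| Section 6 calendar | marked | empty | marked |
| 9.1.1 enrollment list | listed | n/a | n/a |
| 9.2.2 follow-up list | n/a | not listed | n/a |

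The two laboratory lists confirm the calendar independently.

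**2. How much of the course does the second prescription cover?** Inputs: a 9-month course (5.0), taken as 274 days from the initial visit; month 3, taken as day 91; a window of 21 days either side (Section 6).

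- Earliest visit: 91 − 21 = day 70. Latest: 91 + 21 = day 112.
- Share of the course before the visit: 70/274 = 25.5% to 112/274 = 40.9% (nominal 91/274 = 33.2%).
- Days remaining: 274 − 112 = 162 to 274 − 70 = 204, or about 5.3 to 6.7 months.

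**3. How many pregnancies might be involved?** The documents give neither the share of women of child-bearing potential nor a pregnancy rate. Assumed here: 15% to 25% of the 40 statin-arm patients (target enrollment, Section 20), and 2% to 8% pregnancies per woman-year.

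- Women: 40 × 0.15 = 6 to 40 × 0.25 = 10.
- Expected pregnancies = women × (days/365) × rate.

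| Period | Low | High |
|---|---|---|
| Whole course | 6 × 274/365 × 0.02 = 0.09 | 10 × 274/365 × 0.08 = 0.60 |
| Before month-3 visit | 6 × 70/365 × 0.02 = 0.02 | 10 × 112/365 × 0.08 = 0.25 |
| After month-3 visit | 6 × 162/365 × 0.02 = 0.05 | 10 × 204/365 × 0.08 = 0.45 |

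The low and high ends of the last two rows use different visit days, so they need not add to the first row. The middle row is a ceiling on what a month-3 test could find. It counts pregnancies the woman already knows about and assumes that all 40 patients stay on drug, so the yield in unrecognised pregnancies would be smaller.

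**4. Does the existing text detect an unrecognised pregnancy?**

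- History and physical examination are scheduled at months 3 and 9, and physicians evaluate patients at each visit (11.2). These are opportunities to learn of a known pregnancy. Neither includes a test.
- 5.0 permits stopping for any reason, but someone must first know there is a reason.
- The triggers in 11.2 are laboratory abnormalities and symptoms. An early pregnancy need not produce any of them.
- The birth-defect line in 12.2 classifies an outcome. It is not a check before exposure.

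**5. Section 20.** The plan states no figure on this point. Its one design figure, 33 evaluable patients per arm for 0.7 SD, 80% power and two-sided alpha 0.05, reproduces (normal approximation n = 33; noncentral t power 0.7997 at 33). It is not an input here and does not change.

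**The case against.** The strongest reply is that the documents are consistent with one another. Pregnancy is an entry criterion and is checked at entry, and the calendar and both laboratory lists say so. A reader might infer a contradiction between 3.3.5 and the later schedule. The documents do not support that, because an entry criterion does not promise repeat testing.

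A reader might also infer that 3.3.5 exists because of atorvastatin. The text does not say this: the criterion gives no reason, covers both arms, and stands apart from the statin criterion in 3.3.3. Both arms also take warfarin or rivaroxaban (3.2.3), so a test confined to the statin arm cannot be justified by a documented statin-specific hazard. The narrower ground does hold: atorvastatin is the drug the study itself prescribes, and the study chose not to start it in a pregnant participant.

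A third tempting reading is that the trial has no means of handling pregnancy. That goes too far. History, examination, physician review, stopping under 5.0 and the serious-event categories in 12.2 can all act on a known pregnancy. Section 12.5 also has subjects instructed to report adverse events. The consent pages and the Adverse Event form are not visible and may carry pregnancy wording.

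Finally, the month-3 test reaches only conceptions in the first 26% to 41% of the course, and its expected yield is far below one. That stands. It is why the report-and-stop instruction, which covers all 9 months, should carry at least equal weight. What remains is that the two visible lists defining which tests are done both omit the repeat, and none of the mitigating text detects a pregnancy nobody has recognised.

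**Conclusion.** The gap is real but minor. The calendar allows a second atorvastatin prescription, covering 162 to 204 of 274 days, without repeating the check made before the first, and 11.2 gives no explicit instruction if pregnancy occurs.

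The schedule facts and the day counts rest on the documents, apart from the conversion of months to days. The pregnancy counts (0.09 to 0.60 over the course; at most 0.02 to 0.25 findable at month 3) rest wholly on the assumed share of women and the assumed rate, and should be read as orders of magnitude. The argument for change is that the remedy costs almost nothing and could spare an affected participant months of further exposure, not that an event is likely. It is a safety improvement, with no bearing on sample size, power, alpha or the analysis.

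**What to change.** Two parts, of equal weight:

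1. **Section 11.2.** Add that a participant who becomes pregnant, or suspects it, reports this at once; that atorvastatin is then stopped; that the event goes through the reporting route in 12.5; and that she remains in follow-up as 5.0 allows. If the consent form or Adverse Event form already says this, a cross-reference is enough.
2. **Section 6 and 9.2.2.** Mark the existing urine beta-hCG row at month 3 for women of child-bearing potential, at least in the statin arm, with the result read before the second prescription is written. Add the matching line to 9.2.2.

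Cost: one or two sentences, one calendar mark, one list entry, and about 6 to 10 urine strips in the statin arm under the assumed 15% to 25%. Testing both arms would take 80 × 0.15 = 12 to 80 × 0.25 = 20. No extra visit or blood draw is needed, and Section 20 does not change. The limitation is that conceptions after month 3 are reached only by part 1.

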### **3.4 Enrollment/registration of patients**

- 3.4.1 Patients must give written informed consent prior to enrollment on this study. Informed consent may be obtained by the principal investigator, co-investigators, or one of their designees.

### **4.0 Randomization of Patients**

Patients will be randomized at the time of registration/enrollment on this clinical trial via contact with the study nurse/coordinator at the time of the initial registration of the subject. The study nurse/coordinator will conduct the randomization on the REDCap Data Capture system and relay this information to the treating/enrolling physician so that the appropriate medication (atorvastatin) can be started.

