## Schema

## 1.0 Objectives

*This will be a single-center, open-labelled, pilot study. This study has the following objectives:*

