### 1.1 Primary Objective

1.1.1 To determine the reduction of thrombin peak concentration and/or endogenous thrombin potential measured by Thrombin Generation Assay (TGA) at 3 months in the “anticoagulation +atorvastatin” arm as compared to the “anticoagulation” arm.

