### **3.2 Inclusion Criteria**

- 3.2.1 At least 18 years old
- 3.2.2 A diagnosis of proximal DVT (proximal to and including popliteal vein), with or without PE, confirmed by objective imaging studies, such as Doppler ultrasound, venograms (for DVT) and/or computer tomography, angiograms, ventilation-perfusion scan (for PE)
- 3.2.3 Treated with warfarin or rivaroxaban as anticoagulation (short-term bridging with heparin or lovenox, if needed is allowed)

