**20.0 Statistical Analysis**

At least 66 evaluable patients will be randomized (1:1 allocation, 33 evaluable patients in each arm) into "anticoagulation" versus "anticoagulation +atorvastatin" arms. The primary endpoints are thrombin peak and thrombin generation. Based on the published data, we anticipate an 80% power to detect an effect size of 0.7 standard deviations in the reduction of thrombin peak or thrombin generation between the two arms with two-side alpha of 0.05 using a two-sample t test. An overall alpha of 0.1 for this pilot study was split into 0.05 for each endpoint (thrombin peak and thrombin generation) using Bonferroni method. Considering possible drop-outs, our target enrollment will be 80 patients, with 40 on each arm.

All data will be collected on study-approved data collection forms and entered into Research Electronic Data Capture (REDCap), which is a secure, web-based application designed to support data capture for research studies by building and managing online surveys and databases. The system was built with the help of the OSU Research Informatics Services.

Descriptive statistics (i.e. means, standard deviations, 95% confidence intervals for continuous variables, and frequencies for discrete data) and graphical analyses will be used for all clinical outcomes, demographics, VTE related events, laboratory results, and adverse events for each arm. The secondary endpoints will be compared between the two arms using chi-square test or Fisher's exact test, whichever is appropriate. The associations between treatment type and the change in biomarkers will be evaluated using two-sample t test. Log-transform will be used if necessary. Linear mixed models will be used to study the associations between the primary endpoints and treatment, and trend across time. The interaction term "arm x time" will be included in the model to study whether the two treatment arms have different "behavior" across time. Potential confounders will be included in the models. Thrombin peak concentration and

endogenous thrombin potential at 9 months will be compared between the patients on anticoagulation and those off anticoagulation.

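### The 3-month thrombin endpoints are measured on either of two anticoagulants, but the agent is not a stratification factor, need not be recorded before allocation and is not a named covariate

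*Combined protocol and SAP*

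**What the plan says.** - Section 1.0 describes the design: "This will be a single-center, open-labelled, pilot study".
- Section 1.1 sets the primary objective: "To determine the reduction of thrombin peak concentration and/or endogenous thrombin potential measured by Thrombin Generation Assay (TGA) at 3 months", atorvastatin plus anticoagulation against anticoagulation alone.
- Criterion 3.2.3 admits patients "Treated with warfarin or rivaroxaban as anticoagulation (short-term bridging with heparin or lovenox, if needed is allowed". Two oral agents are therefore permitted, and a patient may still be on bridging at entry.
- Section 4.0: "Patients will be randomized at the time of registration/enrollment on this clinical trial via contact with the study nurse/coordinator". The coordinator randomises in REDCap and must then "relay this information to the treating/enrolling physician so that the appropriate medication (atorvastatin) can be started". The section names no stratification factor, no block scheme and no data to be entered first.
- The Section 6.0 calendar lists "Medical/treatment history" at all three visits. It does not name the anticoagulant or tie the entry to a time before allocation.
- Section 20.0 bases the sample size on an unadjusted two-sample t test. For the mixed models it adds "Potential confounders will be included in the models", without naming any. It also plans a comparison in which peak and "endogenous thrombin potential at 9 months will be compared between the patients on anticoagulation and those off anticoagulation". It plans no comparison by agent.

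**The concern.** Thrombin peak and endogenous thrombin potential (ETP) are measured in plasma from anticoagulated patients, and Section 16.0 describes no step that removes the drug's effect from the sample. The planned 9-month comparison on and off anticoagulation shows that the authors expect anticoagulation to matter to these measurements. If the two agents affect the assay differently, the agent is a prognostic variable for both primary endpoints.

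Two things follow when such a variable is neither stratified nor adjusted for. Its between-patient variation stays in the error term and costs power. In a trial of this size the arms can also differ noticeably in mix by chance, which moves the observed statin contrast in that one trial.

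A third, narrower issue is timing. If the agent is not on record before the arm is released, then for a patient still on bridging the recorded agent may have been settled with the arm known. It would then no longer be a clean baseline covariate.

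**Working it through.** **1. The plan's own figure.** Inputs from Section 20.0: 33 evaluable per arm, effect 0.7 SD, two-sided alpha 0.05, two-sample t test. Noncentrality = 0.7 × √(33/2) = 2.84 on 64 df, which gives power 79.97%. Solving for 80% gives 33.02 per arm. The stated design reproduces. Enrolling 80 for 66 evaluable implies 1 − 66/80 = 17.5% drop-out.

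**2. Chance imbalance without stratification.** The share p on one drug is not in the documents; assume 30% to 50%. The SD of the between-arm difference in share is √(2p(1−p)/33). A difference of 15 points or more means at least 5 patients of 33 (5/33 = 15.2%); 20 points or more means at least 7 (7/33 = 21.2%). Exact binomials give:

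| p | SD of difference | 15 points or more | 20 points or more |
|---|---|---|---|
| 0.30 | 0.113 | 22.6% | 8.0% |
| 0.50 | 0.123 | 26.8% | 10.9% |

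**3. Power lost by ignoring the agent.** Let D be the difference between agents on the endpoint, in within-drug SDs. D is an assumption. With a 50/50 mix the total SD is √(1 + D²/4). Take the plan's 0.7 as total SDs. An analysis adjusted for the agent then sees an effect of 0.7 × √(1 + D²/4) within-drug SDs:

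| D | Total SD | Adjusted effect | Power, 33 per arm |
|---|---|---|---|
| 0 (or unadjusted) | 1.000 | 0.700 | 80.0% |
| 0.5 | 1.031 | 0.722 | 82.3% |
| 1.0 | 1.118 | 0.783 | 87.9% |
| 1.5 | 1.250 | 0.875 | 93.8% |

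For scale, at D = 1 a 15-point imbalance moves the unadjusted contrast by 0.15/1.118 = 0.13 total SD, or 0.134/0.7 = 19% of the planned effect. By chance alone its direction is random.

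**4. What an arm-driven shift would do, if there were one.** Bias = shift in mix × D. The false-positive rate comes from the noncentral t, with 33 per arm, a 50/50 pooled mix and nominal 5% per endpoint. Both factors are assumed.

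| Shift | D = 0.5 | D = 1.0 | D = 1.5 |
|---|---|---|---|
| 10 points | 0.05 SD, 5.4% | 0.09 SD, 6.5% | 0.12 SD, 7.7% |
| 20 points | 0.10 SD, 6.7% | 0.18 SD, 11.1% | 0.24 SD, 16.2% |

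Biases are in total SDs. At D = 1 a 5-point shift gives 0.05/1.118 = 0.045 SD and a rate of about 5.4%. The documents say nothing about which row, if any, applies.

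**The case against.** A reader might infer more: that the physician who is told the arm also manages the anticoagulant, steers its choice accordingly, and so biases the primary endpoint. The documents do not support that reading.

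- Criterion 3.2.3 requires treatment with one of the two agents at entry, so the choice ordinarily precedes randomisation. Only patients still on bridging and later switchers can move, and the size of neither group is given. Shifts of 10-20 points across the whole trial would be large for such a group.
- No passage says that the physician told the arm chooses or manages the anticoagulant. Section 8.0 leaves management of recurrent VTE to the treating physician, which makes the inference plausible but does not establish it. Nor does any passage suggest why allocation to atorvastatin would influence the choice.
- Telling the physician the arm is inherent in an open-label trial and is not itself a defect.

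Three further points limit what remains. Chance imbalance is random variation already covered by the t test's error rate, so it is not bias. The endpoint is worded as a reduction and the assay is run at baseline. If change is analysed, part of a stable drug difference cancels for patients already on their oral agent at the first draw, and the gain from adjustment is then smaller. Treatment history and the unnamed confounders give partial cover.

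All of this stands. It narrows the point to precision, balance and a clean baseline record. It does not supply the missing specification: the agent is nowhere required before allocation, stratified on or named as a covariate.

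**Conclusion.** The point holds as a gap in design efficiency and specification. The agent is a likely source of variation in both primary endpoints, and the plan neither balances it nor commits to adjusting for it. An imbalance of 15 points or more would arise by chance in 23-27% of trials, assuming 33 per arm and 30-50% on one drug. Adjustment would raise power from 80% to about 82-94%, assuming agents 0.5-1.5 within-drug SD apart, a 50/50 mix and a planned effect of 0.7 total SD. If the agents do not differ on the assay, there is no gain.

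A claim that randomisation no longer protects the comparison goes too far. Bias from choices made with the arm known is possible for patients on bridging and for switchers, but the documents give neither the number of such patients, the shift in mix nor the gap between agents. The false-positive rates in step 4 illustrate a mechanism and do not estimate this trial's error rate.

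**What to change.** **Section 4.0.** The coordinator enters the current or intended oral anticoagulant (warfarin or rivaroxaban) in REDCap before the arm is displayed. REDCap then randomises 1:1 within these two strata, using random block sizes.

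**Section 20.0.** Include this pre-randomisation stratum as a covariate in the primary 3-month comparison of thrombin peak and ETP. Use the stratum as entered, because the agent actually taken at 3 months may itself have been affected by allocation and adjusting for it would not be a safe substitute.

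**Follow-up.** Record the agent in use at each thrombin generation draw and tabulate switches by arm. This makes switching after allocation visible. It does not prevent switching or remove any bias from it.

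**Cost.** One extra REDCap field, a two-stratum allocation table, and slightly more predictable allocation, which random block sizes limit. The sample size is unchanged. Stratification can apply only to patients not yet randomised. Nothing here bears on which anticoagulant a patient should receive.
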